2. STUDY SUMMARY

Health care personnel (HCP) frequently receive annual influenza vaccinations and a substantive proportion of them might have attenuated or no response to additional standard dose influenza vaccines. In this population that is seasonally exposed to influenza illnesses and repeatedly vaccinated using standard dose (SD) vaccines, adjuvanted (AD) vaccines might elicit a better immunity than the typically used SD. We therefore propose to conduct a double-blinded randomized controlled vaccine trial among HCPs to determine if AD influenza vaccines generate superior seroprotection against influenza than SD vaccines particularly among previous sub-optimal responders.

The trial will be conducted at two hospital sites in Lima-Peru during the 2022 influenza season. It has annual circulation int the country, but with increases during the months of June to October, which coincides with winter. The study is aimed to HCP who were enrolled in the Cohort study of Influenza and other Respiratory Viruses among HCP in Peru (approximately 1500). The number of participants to be enrolled is 800 approximately. The study design is a randomized, double-blind vaccine trial. Eligible HCP at each site who consent to participate will be randomized 1:1 to receive either a single dose of AD (FLUAD, quadrivalent, Seqirus) or SD (VaxigripTetra, quadrivalent, Sanofi-Pasteur). Participants, researchers and laboratory staff performing the assays will be blinded to the vaccine information.

Participants will be invited to attend the study site for a study screening and assessment of eligibility criteria, if they agree to participate and once consent form is signed, they will visit the site at day 0 for vaccination and medical assessment. Another brief medical adverse event assessment will be performed on days 3 and 7. Participants will be also prompted to begin active surveillance for acute illnesses as soon as US Center of Prevention and Control of Disease (US CDC) and the study site PI confirm that seasonal influenza is circulating locally or there are indicators that circulation is imminent. During the influenza season, participants will be followed up twice a week via SMS or phone calls to assess if they become sick with a respiratory event, if so, they will be asked questions about their illness through an acute illness survey and a swab sample will be requested.

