10.2 Sample size

We calculate that we will need a minimum sample size of 118 participants per vaccination group for detecting a difference between two proportions (based on seroprotection percentages for influenza A(H1N1p) of a previous study:91% vs 78% [21]) (see below), considering a 95% confidence level (two-sided) and 80% statistical power. To account for loss to follow up, we will increase sample size by 20%, so sample size will be a minimum of 142 subjects per group (Table 1).

Table 1. Sample size calculation based on published seroprotection rates for different influenza viruses

Seroprotection	P1 (AD group)	P2 (SD group)	n/per group	With additional 20%
subtypes				
Influenza A(H1N1p)	91%	78%	118	142
Influenza A(H3N2)	No information	No information		

Influenza B	No information	No information		
Where P1=percentage o	f seroprotection for AD g	roup and P2=percentage	e of seroprotection for S	D group

However, although the sample size calculation yields 142 participants per group, there may be different scenarios in which the difference between groups is shortened. In the following table, differences of 10-20% are estimated (Table 2). As a result of this calculation, it is estimated that a sample size of approximately 400 individuals per group will allow us to detect a difference of at least 10% considering a 78% seroprotection rate in the group vaccinated with non-adjuvant vaccine.

Table 2. Different scenarios in seroprotection rates (28 days post-vaccination) per group and sample size calculation

Seroprotection rate in SD group	Relative increase (5) in AD group vs SD group	n per group	Total n	With additional 20%
78%	10%	359	718	862
78%	20%	70	140	168
88g%	10%	131	262	314
88%	15%	58	116	140

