 start of the contraceptive method.
- All screening subjects will be assigned a screening subject identification number and listed in a screening log. Those subjects remaining eligible after the physical exam and evaluation of screening will be enrolled and be given a subject enrollment number prior to be immunized.

Study staff will provide participants with a copy of the informed consent as well as an informative brochure including information of the study, investigational product, and contact information of study staff and schedule of activities (Appendix D). We anticipate to recruit up to a maximum of 800 participants in the study, 400 per group. The informed consent will include permission to access medical records and link data from the previous study with data from the current study.

Subjects who fail screening may be re-screened if the Investigator thinks it is likely the subject will fulfill the inclusion/exclusion criteria requirements at a later time.

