10.10 Withdrawal of Subjects from the Study

Every reasonable effort should be made to ensure that each subject complies with the protocol and completes all study visits. However, a subject may voluntarily withdraw or be withdrawn involuntarily from participation if:

- The subject withdraws consent.
- The investigator recommends discontinuation in the interest of the subject's safety (i.e., adverse event related) or because of significant and irremediable protocol non-compliance.
- CDC, NAMRU6, the IRB terminates the clinical trial for safety or other reasons.

Any adverse event leading to early discontinuation will be followed to resolution. No subject prematurely withdrawing/withdrawn will be replaced.

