10.13 Study outcomes

The primary outcome to be measured will be seroconversion at day 28 after vaccination. Seroconversion will be defined as having a haemagglutination inhibition (HI) geometric mean titre (GMT) of \geq 1:40 in the case the pre-vaccination HI GMT <1:10 or having a four-fold rise in titre in the case the pre-vaccination HI GMT \geq 1:10. We will also measure HI GMT at the end of season. Seroprotection will be defined as having an HI GMT \geq 1:40.

Other outcomes that will be measured include:

-reactogenicity to vaccination

-acceptability of AD influenza vaccination

-acute respiratory illness (ARI)

-ARI-associated outcomes (absenteeism, medical visits, hospitalization, other)

-laboratory-confirmed influenza and other respiratory pathogens

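### Section 10.2: 400 enrolled per group does not carry the plan's own 20% loss allowance for the 10% increase it claims to detect, and Table 2's sample sizes do not match their row labels

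*Combined protocol and SAP*

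**What the plan says.** Section 10.2 sizes the trial on seroprotection, "considering a 95% confidence level (two-sided) and 80% statistical power". Table 1 takes 91% (AD) vs 78% (SD) for A(H1N1p) and gives 118 per group, or 142 after the loss allowance. The allowance is worded as follows: "To account for loss to follow up, we will increase sample size by 20" percent.

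The section then considers smaller differences in Table 2, whose effect column is headed "Relative increase (5) in AD group vs SD group":

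| SD rate | Increase | n per group | Total | Total with 20% added |
|---|---|---|---|---|
| 78% | 10% | 359 | 718 | 862 |
| 78% | 20% | 70 | 140 | 168 |
| 88% | 10% | 131 | 262 | 314 |
| 88% | 15% | 58 | 116 | 140 |

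From this table the section draws its conclusion: "sample size of approximately 400 individuals per group will allow us to detect a difference of at least 10% considering a 78% seroprotection rate" (SD group).

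Three other places bear on the claim:

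- **Section 10.4:** "We anticipate to recruit up to a maximum of 800 participants in the study, 400 per group". The Study Summary agrees: "The number of participants to be enrolled is 800 approximately".
- **Section 10.10:** "No subject prematurely withdrawing/withdrawn will be replaced".
- **Section 10.13:** "The primary outcome to be measured will be seroconversion at day 28 after vaccination". Table 2 concerns seroprotection, which is not that outcome.

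The stray character in the Table 2 heading, and a similar one in an 88% cell, are treated as typing or extraction slips and not counted as errors.

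**The concern.** The sentence about 400 per group is what justifies enrolling 400 rather than 142 per group, and it is presented as the result of Table 2. The matching row asks for 862 enrolled, which is more than the maximum of 800. So 400 per group covers the number needed before loss (359) but not the number needed after the plan's own uplift (359 × 1.2 = 430.8, so 431).

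The sentence also does not say whether 10% is relative or absolute. Some of the sample sizes in Table 2 cannot be obtained from the increases printed beside them.

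What is at stake is whether the trial has the 80% power it claims for the effect it names, and whether a reader can rely on the table behind that claim.

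**Working it through.** **Inputs.** Two-sided 5% level, 80% power, the Table 1 and Table 2 rates and the 20% uplift come from Section 10.2. The maximum of 800 comes from Section 10.4. Allocation is 1:1 (Study Summary).

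**Formula.** Two proportions, normal approximation, unpooled variance, rounded up:

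n per group = (1.960 + 0.842)² × [p1(1−p1) + p2(1−p2)] / (p1−p2)², where (1.960 + 0.842)² ≈ 7.85.

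**Step 1: reproduce Table 1.** For 91% vs 78%: 7.85 × (0.0819 + 0.1716) / 0.13² = 117.7, so 118. This matches, which identifies the method. The uplift is a multiplication: 118 × 1.2 = 141.6, so 142.

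**Step 2: find what produces the Table 2 values.** The same formula returns all four printed values, but only for these AD rates:

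| Contrast | n per group | True relative increase | Label |
|---|---|---|---|
| 78% vs 86% | 359 | 10.3% | 10% |
| 78% vs 94% | 70 | 20.5% | 20% |
| 88% vs 97% | 131 | 10.2% | 10% |
| 88% vs 100% | 58 | 13.6% | 15% |

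**Step 3: recompute at the labelled increases.**

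| Label | AD rate | n per group | Total | Total × 1.2 | Printed n |
|---|---|---|---|---|---|
| 78% + 10% | 85.8% | 379 | 758 | 910 | 359 |
| 78% + 20% | 93.6% | 75 | 150 | 180 | 70 |
| 88% + 10% | 96.8% | 139 | 278 | 334 | 131 |
| 88% + 15% | 0.88 × 1.15 = 101.2% | impossible | – | – | 58 |

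Pooled, continuity-corrected, arcsine, one-sided and 90%-power versions were also tried. None reproduces the table from its labels.

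**Step 4: test the absolute reading.** For 78% vs 88%: 7.85 × (0.1716 + 0.1056) / 0.10² = 217.6, so 218. The printed 359 therefore cannot represent ten percentage points.

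**Step 5: compare with the cap.** 718 × 1.2 = 861.6, so 862, which exceeds 800. At the exact label, 758 × 1.2 = 909.6, so 910, which also exceeds 800.

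**Step 6: power at 800 enrolled.** Power = Φ(|p1−p2| / √{[p1(1−p1) + p2(1−p2)]/n} − 1.960). Undoing the uplift gives 800 / 1.2 / 2 ≈ 333 evaluable per group. For 78% vs 86% at n = 333: 0.08 / √(0.2920/333) = 2.70, and Φ(2.70 − 1.96) = 0.771.

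| Evaluable per group | 78% vs 85.8% | 78% vs 86% | 78% vs 88% | 78% vs 91% | AD rate giving 80% power |
|---|---|---|---|---|---|
| 400 (no loss) | 82.1% | 84.2% | 96.7% | 99.9% | 85.6% |
| 333 (plan's × 1.2) | 74.8% | 77.1% | 93.4% | 99.7% | 86.3% |
| 320 (20% actually lost) | 73.1% | 75.4% | 92.5% | 99.6% | 86.4% |

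The pooled formula changes the powers at 333 per group for 85.8% and 86% by less than half a point (74.5% and 76.8%).

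**Step 7: loss that can be tolerated.** 80% power is kept up to 1 − 359/400 = 10.25% loss (AD rate 86%), or 1 − 379/400 = 5.25% (AD rate 85.8%).

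**The case against.** The best defence is that the sentence gives no scale. The text just before it discusses 91% vs 78%, a 13-point gap that might shrink, so ten percentage points is a natural reading. On that reading 218 per group is enough and power after the allowance is 93%. This shows that the scale must be stated, but it does not rescue the sentence as written. The sentence is offered as the outcome of a table of relative increases whose 359 cannot be a ten-point contrast.

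Second, with 400 evaluable per group the claim is true (82% or 84%), and the plan says approximately. That holds only before loss. Section 10.4 makes 400 the enrolment maximum, and the plan applies its uplift in both tables.

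Third, the three sample-size mismatches come from rounding the AD rate to a whole percent, not from a wrong formula. That is correct, and showing the AD rates would be enough to cure it. It does not explain the fourth row.

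Fourth, the consequence is small and 800 far exceeds the Table 1 requirement. That stands, and it limits the point to the stated power and the table.

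Finally, restated seroprotection power is still not power for the primary analysis. Section 10.13 makes seroconversion primary, and Section 11.1 names a Wilcoxon signed-rank test. That is true; the correction here should at least name the endpoint it refers to.

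**Conclusion.** The concern holds. On the scale used in Table 2, 800 enrolled does not give 80% power for a 10% increase over 78% once the plan's own allowance is applied. Power is about 77% (AD rate 86%) or 75% (85.8%), and 80% is reached only at about 86.3%, which is 8.3 points or 10.6% relative. If 20% were actually lost, power would be 75% or 73%.

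Separately, three rows of Table 2 understate n for their labels by 5 to 7% of the printed value (359 against 379, 70 against 75, 131 against 139), and the 88% with 15% row is impossible.

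These figures assume a two-sided 5% two-proportion z-test on seroprotection and equal loss in the two groups. The documents give no expected loss other than the 20%. If loss stays near 10% or below, the 86% scenario keeps 80% power. The stated power and Table 2 should be corrected; the choice of 800 need not change.

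**What to change.** Keep 800 and replace the sentence in Section 10.2 with wording to this effect:

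> For seroprotection, 800 participants will be enrolled. Allowing for the 20% uplift, about 333 per group are expected to be evaluable. This gives 80% power for 78% vs about 86.3%, and about 75% power for 78% vs 85.8% (a 10% relative increase). If 20% are lost (320 per group), 80% power is reached at about 86.4%.

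The last sentence is an optional sensitivity statement. Name seroprotection explicitly, because the primary outcome is seroconversion.

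In Table 2, add a column with the AD rate and state that the increase is relative. Then do one of the following:

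- correct n per group / total / total with 20% to 379/758/910, 75/150/180 and 139/278/334; or
- keep the printed values and label those rows 86%, 94% and 97%.

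Remove the 88% with 15% row, or relabel it 88% vs 100%.

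The cost is a text and table correction and a slightly less favourable stated power. No participants are added and the design does not change.

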10.3 Pre-enrollment procedures

Study staff will contact all HCP who participated of a vaccine effectiveness study at the two participant hospitals to identify potentially eligible subjects and invite them to participate in the vaccine trial. After a brief description of general aspects of the study, field workers will check if potential eligible subjects, aged \geq 18 years, will be available during the study period, been able to attend the study clinic for scheduled visits, have valid personal identification forms, and may be interested to consider participation in the study. (Appendix A) Those interested will be invited to come to the study clinic where the study doctor will explain individually and in detail the study and ask them to sign and written informed consent form if they agree to participate.

10.4 Screening/Enrollment Procedures

Enrollment will begin. during influenza season in Peru[23].

Potential volunteers will come to the study clinic for a screening visit at which time they will be invited to sign a written informed consent form. (Appendix C). Prior to any study procedure the investigator or the health care provider designated, will provide each volunteer sufficient time to read the informed consent document and will fully inform the subject of the nature and scope of the study, potential risks and benefits of participation, the study procedures involved, and will answer all questions for the subject prior to requesting the subject's signature on the informed consent form (ICF). A signed ICF will be obtained prior to performing any study-related procedures.

Once the ICF signature has been obtained, the following screening procedures and assessments will be performed and results recorded on the CRF:

- Assignation of screening number
- Inclusion and exclusion criteria review (Appendix B)

- Demographic documentation including including age, sex, race, ethnic origin, height, and weight. Medical documentation: medical history and nature of contact with patient (Appendix E)
- A complete physical examination including head, eyes, ears, nose, and throat (HEENT), heart, lungs, abdomen, skin, lymph nodes, neurological, musculoskeletal systems
- Vital signs including heart rate(HR), blood pressure (BP), respiratory rate (RR), and oral temperature
- All women will have a reproductive status assessment and women with child bearing potential will
 have a urine pregnancy test. It will be performed considering a period of 5 weeks after the last
 menstrual period. Women of reproductive status will be asked about the type of contraception she
 currently uses. If she is not using any form of secure contraception, she will be offered to attend an
 appointment in the family planning program from each hospital. As part of that program she will be
 offer to choose oral or injectable contraception, free of charge, or an alternative secure contraception
 that could be applied in a family planning clinic (like and intra-uterine device). If the family planning
 clinic for any reason does not have the method in stock (oral, injectable or barrier), the study will
 provide it. She can return to be re-screened for the trial once appropriate contraception use has been
 demonstrated and/or documented. She may be re-cheduled in the range of 1 to 4 weeks after the
 start of the contraceptive method.
- All screening subjects will be assigned a screening subject identification number and listed in a screening log. Those subjects remaining eligible after the physical exam and evaluation of screening will be enrolled and be given a subject enrollment number prior to be immunized.

Study staff will provide participants with a copy of the informed consent as well as an informative brochure including information of the study, investigational product, and contact information of study staff and schedule of activities (Appendix D). We anticipate to recruit up to a maximum of 800 participants in the study, 400 per group. The informed consent will include permission to access medical records and link data from the previous study with data from the current study.

Subjects who fail screening may be re-screened if the Investigator thinks it is likely the subject will fulfill the inclusion/exclusion criteria requirements at a later time.

10.5 Allocation of subjects

We will randomly allocate consented subjects to either receive standard or adjuvanted influenza vaccination following a blocked randomization methodology to balance the number of participants in two study arms [24]. The electronic data capture system that will be used named REDCap, includes a tool that will allow randomization.

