5. LOCATION

The study will be performed at two tertiary hospitals in Lima, Peru: Cayetano Heredia National Hospital, and Arzobispo Loayza National Hospital. The two hospitals were selected because have previously participated of an influenza vaccine effectiveness cohort study among healthcare personnel (HCP) and contributed 1,500 participants.

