10.8 Surveillance monitoring

An *acute illness¹* is defined as one or more of the following symptoms within the past 7 days: cough, runny nose, body aches, or feverishness (could be not measured fever). The focus of the study is on acute or newly worsened symptoms; this will be emphasized in the phrasing of screening questions, orientation to

¹Sources for this method and similar items can be found in the following manuscripts:

Irving et al. (2011) Comparison of clinical features and outcomes of medically attended influenza A and influenza B in a defined population over four seasons: 2004–2005 through 2007–2008. Influenza and Other Respiratory Viruses DOI: 10.1111/j.1750-2659.2011.00263.x

participants, and staff training. Nonetheless, participants will be discouraged from assuming they know the source of symptoms or dismissing symptoms they might attribute to allergies or non-infectious sources, since the study intends to assess all acute illnesses regardless of presumed etiology. Following are active surveillance steps.

- a. Starting at enrollment, reports of acute illness pre-season will be acknowledged by study staff but will not prompt respiratory specimen collection;
- b. During the approximately 10-20 weeks of local influenza circulation, participants will receive twiceweekly communication via cellphone messaging (e.g. *WhatsApp*) or phone call to confirm whether they have acute illness symptoms;
- c. During follow up participants will be asked to contact study staff immediately by cellphone messaging (e.g. *WhatsApp*) or telephone when they experience symptoms of acute illness; when possible, some facilities will check staff schedules to identify participants who might have missed work because of illness in order to proactively contact them;
- d. Participant reports of symptoms will be logged by study staff in a "Symptom Screening Log" (Appendix K);

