10.8.4 Timing of Active Surveillance

We will refer to historical patterns for the start and end of local influenza circulation in planning study milestones. We will also monitor all available sources (e.g. NAMRU-6 influenza surveillance, INS-MOH) of local surveillance for laboratory-confirmed influenza virus infections, allowing for starting surveillance up to two-four weeks prior to typical influenza circulation. Participants will be prompted to begin active surveillance for acute illnesses as soon as US CDC and the study site PI confirm that seasonal influenza is circulating locally or there are indicators that circulation is imminent. Participants will also be notified when local influenza circulation or the season has ended via SMS message, an email, or a telephone call, based on the same epidemiological data used to trigger the start of the season.

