10.9.1. Blind opening contingency plan Masking (blinding)

Only in the event of an emergency or serious adverse event or other particular event that alters the riskbenefit profile of the intervention will the principal investigator determine whether unmasking of a participant's study intervention assignment is justified. The safety of the participants should always be the first consideration when making such a determination. If the investigator decides that opening the blind is warranted, the investigator should make every effort to communicate such a decision by telephone or mail to the sponsor or medical monitor prior to unmasking a participant's treatment assignment, unless this can delay the process of opening the participant's assignment, since it is necessary to have the approval of one of them in order to be able to communicate with the person responsible for the randomization, who has access to the central randomization lists by Code of each participant, and thus request such information.

The date and reason why the blind was broken must be recorded in the source documents and in the CRFe by the investigator of the research center.

If the treatment allocation blind is opened, this information should only be shared with the other medical researchers of the center when it is necessary to know it (especially when the cause is a safety event that corresponds to a serious adverse reaction). Information about treatment allocation should not be shared with other people.

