5) To evaluate laboratory-confirmed influenza illness rates in the group receiving AD influenza vaccination compared to the group receiving SD influenza vaccination. Using data collected through active surveillance, we will calculate incidence densities and use descriptive statistics and Z-test to assess differences in the proportion of HCPs who had laboratory-confirmed influenza (as determined by PCR on nasal swab samples) during the period of the clinical trial among the HCP who received the influenza vaccines AD vs. SD. A Cox regression model will be used to adjust the risk of developing influenza between both groups according to demographic and occupational characteristics. Health personnel participating in the clinical trial will be included as a study population for these analyzes.

6) To assess the adverse events among HCP receiving SD and AD influenza vaccines. Using data collected through active surveillance, we will use descriptive statistics and the Z test to assess the differences in the proportions of adverse events (anticipated and serious) between the HCP who received the AD and SD

influenza vaccines. All health personnel participating in the clinical trial will be included as a study population for these analyzes.

Table 1: Summary of Analysis by Endpoints and Analysis Populations.

OBJECTIVE	VALUATION CRITERIA	STATISTICAL TEST	POPULATION OF ANALYSIS
Primary Efficacy Analysis			
To determine if the AD influenza vaccine generates superior immunogenicity than the vaccine against SD influence without adjuvant among the HCP.	Immunogenicity - superior serumconversion of AD vaccine versus SD vaccine in HCP.	Wilcoxon signed rank test.	PP population
Secondary Efficacy Analysis			
To compare the post-vaccine immune response, in approximately 28 days after vaccination and at the end of the influenza season, among the HCP with a history of influenza infection confirmed by PCR result during any of the 6 years during the previous cohort study (2016 to 2021).	Post-vaccination immune responses, approximately 28 days after vaccination and at the end of the season, among HCPs with a history of PCR-confirmed influenza infection	Wilcoxon signed rank test.	ITTm1

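### The plan does not say whether randomisation blocks are kept within hospital, and no analysis names site; stratifying by hospital would be a small, nearly free improvement, most useful for objectives 3 to 5.

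*Combined protocol and SAP*

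**What the plan says.** Section 5 (Location): "The study will be performed at two tertiary hospitals in Lima, Peru". Section 10.4 sets a "maximum of 800 participants in the study, 400 per group" and gives no split by hospital.

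Three places bear on allocation:

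- Section 2 (Study Summary): "Eligible HCP at each site who consent to participate will be randomized 1:1".
- Section 10.5: subjects are allocated "following a blocked randomization methodology to balance the number of participants in two study arms". No block size or stratification factor is given.
- Section 10.9.1, on emergency unblinding, mentions the person "who has access to the central randomization lists by Code of each participant". It does not say whether those lists are separate by hospital.

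No analysis in section 11.1 names site:

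- The primary comparison and objectives 1 and 2 have no covariate or stratum.
- The logistic model (objective 3) and the generalised linear models (objective 4) list person-level factors: age, sex, chronic disease, body mass index, smoking and alcohol. Objective 4 also examines earlier influenza and earlier vaccination.
- The Cox model (objective 5) adjusts "according to demographic and occupational characteristics".

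On illness surveillance, section 10.8 says that, where possible, "some facilities will check staff schedules to identify participants who might have missed work because of illness". Section 10.8.4 has active surveillance begin "as soon as US CDC and the study site PI confirm that seasonal influenza is circulating locally", or when circulation appears imminent.

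**The concern.** Hospital is a known two-level design factor, and the plan does not settle how allocation or analysis treats it. A programmer could build one list or two from section 10.5 and comply with it either way. What is at stake depends on which was meant and on which analysis is considered:

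- Blocks within hospital, analysis ignoring hospital: the standard error of the arm difference is too large, so the tests are conservative.
- Blocks ignoring hospital: the arms can differ by chance in their hospital mix. The unadjusted test remains valid but is less precise than a stratified one.
- Objectives 3 and 4: prior vaccination and the other risk factors are not randomised. If they and the immune response both differ by hospital, the estimates are confounded.
- Objective 5: if one hospital looks harder for absent staff, the rate of detected cases differs between hospitals, and a single baseline hazard is a poor description of the data.

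**Working it through.** **Inputs from the documents.** Two sites; 400 per arm (10.4); two-sided 5% level and 80% power; seroprotection 78% with standard vaccine and 91% with adjuvanted vaccine (10.2).

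**Assumptions.** The documents give no hospital split and no difference between hospitals. I take splits of 50:50 and 60:40, gaps in seroprotection between hospitals of 0, 10 and 20 points, and all 800 participants evaluable.

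**Plan's own figure.** With unpooled variances, n = (1.96 + 0.8416)² × (0.91×0.09 + 0.78×0.22) / 0.13² = 7.849 × 0.2535 / 0.0169 = 117.7, so 118 per group; 118 × 1.2 = 141.6, so 142. Both match section 10.2.

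**If blocks ignore hospital (equal sites).**

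- SD of the between-arm difference in the share from one hospital: √(2 × 0.25/400) = 0.0354.
- 95% range: ±1.96 × 0.0354 = ±0.069, about 7 points. A difference of 5 points or more occurs in about 18% of trials.
- Shift in the arm difference at that extreme: 0.069 × 10 points = 0.7 points; 0.069 × 20 points = 1.4 points.
- For comparison, the SE of the arm difference is √(2 × 0.78 × 0.22/400) = 0.029, or 2.9 points.

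**If blocks are within hospital and the test ignores hospital (20-point gap, 68% and 88%).**

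- Variance used by the test: 0.78 × 0.22 = 0.1716.
- Variance within hospitals: (0.68×0.32 + 0.88×0.12)/2 = 0.1616.
- SE ratio: √(0.1716/0.1616) = 1.03, so the SE is about 3% too large.
- Actual type I error: 2 × [1 − Φ(1.96 × 1.03)] ≈ 0.043.

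**Simulation.** 40,000 runs per setting. Power is for 78% versus 85.8% (a 10% relative increase). An unadjusted two-proportion z-test stands in for the planned test and is compared with the Cochran-Mantel-Haenszel (CMH) test stratified by hospital. Equal sites; each cell shows type I error / power:

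| Site gap | Blocks ignore site, unadjusted | Blocks ignore site, CMH | Blocks within site, unadjusted | Blocks within site, CMH |
|---|---|---|---|---|
| 0 | 0.048 / 0.824 | 0.048 / 0.823 | 0.051 / 0.821 | 0.051 / 0.821 |
| 10 points | 0.051 / 0.819 | 0.050 / 0.826 | 0.046 / 0.824 | 0.048 / 0.828 |
| 20 points | 0.051 / 0.818 | 0.050 / 0.847 | 0.044 / 0.828 | 0.051 / 0.847 |

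Monte Carlo error is about 0.001 for type I error, √(0.05×0.95/40,000), and 0.002 for power, √(0.82×0.18/40,000). At a 60:40 split and a 20-point gap, the unadjusted test with within-site blocks has type I error 0.043. Most of the gain comes from the stratified analysis; at a 20-point gap it reaches 0.847 with either kind of block.

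**Illness (objective 5).** With assumed attack rates of 3% to 10% and ratios between hospitals of 1.5 to 3, the 95% chance imbalance moves the arm difference by 0.1 to 0.7 points, against an SE of 1.2 to 2.1 points.

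**Objectives 3 and 4.** The size of any confounding cannot be calculated. The documents do not say how vaccination history or response varies by hospital. The point here is structural: randomisation of vaccine does not protect estimates for factors that were not randomised.

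**The case against.** Several counter-arguments have force.

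- Section 10.5 is silent on site; it does not exclude it. The Study Summary can naturally be read as allocation within hospital, and central lists can be site-specific. This stands, and it is why the two cases are kept apart above: conservatism and chance imbalance need opposite assumptions about the blocks and cannot both be charged to the plan.
- Large gaps between hospitals lack support. Both are tertiary hospitals in one city, recruiting from one cohort under the same criteria, with serology done at the US CDC laboratory. This stands; 20 points is an illustration.
- The covariate list for objectives 3 and 4 is introduced as variables to consider, so it is not closed, and occupational characteristics in the Cox model might include the employing hospital. This stands only in part: neither wording prespecifies site, so the choice could be made after the data are seen.

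A reader might also infer that the two hospitals start surveillance on different dates. The documents do not say so. Section 10.8.4 makes the start a decision of US CDC together with the site investigator, drawing on local surveillance sources, and both hospitals are in Lima. Nor does section 10.8 say that one hospital will check schedules and the other will not. That check comes on top of twice-weekly contact with every participant, so detection may differ but is not shown to.

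**Conclusion.** The plan leaves open whether blocks are within hospital, and no analysis names site. For the randomised comparisons the consequence is small. With within-site blocks, the unadjusted tests are slightly conservative (type I error about 0.043 to 0.044 at an assumed 20-point gap). With blocks that ignore site, type I error is correct (0.048 to 0.051 across the settings run) and a little precision is lost. Stratifying gains about 0 to 3 points of power for assumed gaps of 0 to 20 points.

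It would be tempting to call the 1.4-point shift a bias. It is a chance shift at the edge of its 95% range, under an assumed 20-point gap, and the unadjusted SE already allows for it when blocks ignore site. There is no inflated false-positive risk. Nor does surveillance reach the primary outcome in section 10.13: day-28 seroconversion is determined by serology.

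The better reasons to act are possible confounding by hospital in objectives 3 and 4, whose size cannot be judged from the documents, and possibly different case detection in objective 5. Overall this is a low-priority improvement.

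**What to change.** **Section 10.5.** State that blocks are generated separately within each hospital, and bring sections 2 and 10.9.1 into line.

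**Section 11.1.**

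- Primary objective and objectives 1 and 2: compare seroconversion and seroprotection with a Cochran-Mantel-Haenszel test stratified by hospital. For titres, use a between-group rank test stratified by hospital (van Elteren) or a model with a site term. This replaces the stated Wilcoxon signed-rank test, which is a paired procedure, so the change of test should be made openly.
- Objectives 3 and 4: add site to the models.
- Objective 5: stratify the Cox model by site. Record by hospital when surveillance started and ended and whether staff schedules were checked.

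**Cost.** A few sentences of text and two allocation lists in the data system. With two strata there is no loss of power in the simulation even when the hospitals do not differ (0.82 with or without stratification). If allocation has already been set up, the changes to 11.1 can be made alone and keep most of the benefit.
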